### **3.3 Study Duration, Enrollment and Number of Subjects**

The entire study is expected to last 60 months with each subject's participation lasting 12 months. The targeted enrollment goal is 400 subjects with ~133 subjects randomized to each study arm.

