#### **Objective 1:**

To evaluate the primary outcome by intervention arm, we will use a linear mixed model to conduct an analysis of covariance (ANCOVA), controlling for site type (ED vs. Urgent Care), index visit pain severity, age, gender, race, medical comorbidities (as the Gagne score), baseline intermittent opioid use, a history of chronic pain, and access to a PCP. These control variables were selected *a priori* based on prior evidence of prognostic value and will not be subjected to significance testing. This model will include all BPI-SF average scores (1, 3, and 6) as outcomes, will include fixed effects for group, time, and group-by-time, as well as all of the control variables, and will use an unstructured covariance matrix for the error terms. We will specify a 6 degrees of freedom (df) linear contrast to test the overall null hypothesis of no mean difference in BPI-SF score at any follow-up visit across the 3 groups at the 5% significance level. If the overall null hypothesis is rejected, we will then conduct separate 3 df contrasts to compare each of the intervention groups with the control group using a Bonferroni-adjusted 2.5% significance level. We will estimate mean pairwise differences along with 95% confidence intervals at each time point. Missing BPI-SF data will be ignored for the primary comparison. The primary analysis will be conducted using the ITT Population, but will also be repeated using the PP Population.

We will also conduct a sensitivity analysis of the primary comparisons using a multiple imputation approach. Pain scores for patients taking analgesics in the past week will be imputed using demographic characteristics, history of chronic pain, pain location, pain etiology (traumatic vs. not traumatic), baseline pain severity, analgesics used, and treatment group.

We will use similar ANCOVA models to test the intervention effects on the secondary outcomes. For continuous or ordinal outcomes, we will use generalized estimating equations models and contrast tests. For any binary variables (e.g., opioid use or non-use) we will also use ANCOVA model but will fit mixed-effect logistic regression models.

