**Figure X****Figure Y****Figure Z**

Thus, we created an exemplary dataset in which participants in the full intervention and video-only groups experienced post-randomization mean pain scores of 20% or 15%, respectively, lower than that in the usual care group. We assumed that loss-to-follow-up times would be exponentially distributed such that the total loss would be 20% at 12 months. Under these assumptions, randomizing 120 participants to each group would provide at least 90% power for testing the overall null hypothesis of no difference across the three groups in mean change from baseline to any follow-up visit through the 6-month visit using linear contrast tested at the 5% significance level (Figure Z).

Furthermore, this sample size would provide about 93% power for the comparison between the full intervention and the usual care group and 67% power for the comparison between the video-only group and the usual care group under these same assumptions, each tested at Bonferroni-adjusted 2.5% significance levels. Because we would like our sample size to support both the intention to treat analysis and the per protocol analysis (restricted to non-admitted patients) and assuming that up to 10% of enrolled patients will be admitted, we plan to enroll 400 patients. The sample size is not calculated based on secondary outcomes. In order to avoid selective reporting of secondary outcomes, we will register and report all secondary outcomes regardless of what is found. The MIXED Procedure in SAS, version 9.4 (SAS Institute, Cary, NC) was used for calculations.

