Reducing the Transition from Acute to Chronic Musculoskeletal Pain among Older Adults

(BETTER from Pain)

NCT number NCT04118595

Document Date 07/24/2022

**Reducing the Transition from Acute to Chronic
Musculoskeletal Pain among Older Adults**

(BETTER from Pain Study)

Statistical Analysis Plan

Version 1.1

This statistical analysis plan is an expanded version of the summary analysis plan included in the study protocol and supersedes the summary plan included in the study protocol. Any significant changes made to this analysis plan after study initiation will be documented herein.

1. Study Objectives

The objectives of this 3-arm randomized trial are as follows:

Objective 1: To evaluate the effects of two Shared Decision Making based interventions (full and video-only intervention) relative to Usual Care on musculoskeletal pain (MSP), as measured by the combined pain severity and interference scores from the Brief Pain Inventory Short Form (BPI-SF), through 6 months following the initial visit.

Sub-Objective 1a: To evaluate the intervention effects separately on the two components of the BPI-SF, pain severity and interference, evaluating both longitudinal change through 12 months and differences at discrete time points of 1, 3, 6, and 12 months.

Sub-Objective 1b: To evaluate the intervention effects over time on other key secondary outcomes, including opioid use, analgesic-related side effect frequency and severity, physical function, overall health, sleep quality, and healthcare utilization.

Objective 2: To assess the mechanisms by which the interventions (full and video-only) influence outcomes.

Objective 3: To estimate the incremental cost per case of persistent pain (defined as pain ≥ 4 on 0-10 scale present at one year) prevented by either the full or video-only intervention compared with usual care.

This document describes the analyses planned for Objectives 1 and 2, and other supporting quantitative analyses. The cost-effectiveness analysis to be applied for Objective 3 will be described elsewhere.

2. Study Design Overview

Four hundred patients presenting with acute MSP recruited from four sites (3 emergency departments (EDs) and one Urgent Care) will be randomized to one of three arms:

1. **Full Intervention** (video + telecare + primary care provided (PCP) communication)
2. **Video-only Intervention** (video but no telecare or PCP communication)
3. **Usual Care**

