As an open-label study, participants, providers, and many study staff will know to which group individual participants have been randomized (the Research Assistants who conducted the follow-up interviews were blinded to treatment arm assignment). However, efforts will be made to keep the principal study statistician blinded to randomization group during the course of the trial. Any key decisions regarding study outcomes, the appropriateness of test statistics or model assumptions, changes to this analysis plan, or any other statistical issues will be made in a blinded review of the data (i.e., blinded to the true randomization groups). The generated allocation sequence has been generated by the Lead Data Manager and uploaded to the secure REDCap randomization module. Datasets provided to the principal statistician prior to unblinding will not include randomized treatment assignment. Primary ITT analyses will be initially programmed using dummy (computer generated) treatment assignments. Unblinding with respect to the true randomization groups will only be done for the final interpretation of the results. Membership in the Per-Protocol Population cannot be adjudicated without knowing actual group assignment.

5. Scoring of Outcome Variables and Certain Baseline Control Variables

Many outcome variables and some baseline control variables will be measured using validated scales or indices. The scoring to be used for each of these scales/indices, including handling of missing scale items, is described in this section.

a. The Brief Pain Inventory Short Form (BPI-SF)

The BPI-SF is composed of two sub-scales, one for pain severity and the other for interference. Pain severity is measured using four items to assess pain at its “worst in the past week”, “least in the past week”, “average in the past week”, and “right now”. Each of these is scored on a 0 to 10 scale, with 0 indicating “none” and 10 indicating “worst”. A Pain Severity Score will be obtained using the mean of these four items. If at most one of the four items is missing, we will use item-mean imputation and take the mean of the 3 non-missing items.

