comorbidity score, baseline intermittent opioid use, a history of chronic pain, and access to a PCP (access to a PCP was used to stratify the randomization and, as such, it is important to control for it in all models). These control variables were selected a priori based on prior evidence of prognostic value and will not be subjected to significance testing. This model will include all pain severity scores (1, 3, 6, and 12 months) as outcomes; will include fixed effects for group, visit, and group-by-visit; and will use an unstructured covariance matrix for the error terms. We will first test a 6 degrees of freedom (df) linear contrast of the overall null hypothesis of no mean difference in the primary outcome at any of the 1-, 3-, and 6-month follow-up assessments across the 3 groups at the 5% significance level. If the overall null hypothesis is rejected, we will then conduct two separate 3 df contrasts to compare each of the intervention groups with the control group using a Bonferroni-adjusted 2.5% significance level. We will secondarily estimate mean pairwise differences along with 95% confidence intervals at each time point, including data collected at the 12-month follow-up time point.

10. Secondary and Exploratory Analyses (Objective 1)

The same linear mixed modeling approach used for the primary outcome will be applied to each of the separate components of the BPI-SF (Pain Severity and Interference). Similar comparisons using the sequence of linear contrasts and 95% confidence intervals as specified for the primary outcome will be made.

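### The 2.5% level for the two comparisons with usual care is valid, but it is not needed behind the 5% three-arm test and costs about 9 points of video-only power

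*SAP*

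**What the plan says.** SAP section 9 sets a two-step test of the primary outcome. Step one: "We will first test a 6 degrees of freedom (df) linear contrast of the overall null hypothesis", covering all three groups at months 1, 3 and 6, at the 5% level. Step two is reached only on rejection. It uses two 3-df contrasts to "compare each of the intervention groups with the control group using a Bonferroni-adjusted 2.5% significance level". The protocol has the same rule in the synopsis and in section 6.1 under Objective 1 ("using a Bonferroni-adjusted 2.5% significance level").

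Protocol 6.2 gives power at 120 per arm: about 93% for full intervention versus usual care and "67% power for the comparison between the video-only group and the usual care group", "each tested at Bonferroni-adjusted 2.5% significance levels". It gives at least 90% for the overall test. Protocol 3.3 then says: "The targeted enrollment goal is 400 subjects with ~133 subjects randomized to each study arm".

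Neither document says why both the gate and the Bonferroni split are used.

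**The concern.** The gate and the Bonferroni split each protect against the same error, a false claim when two comparisons share one control arm. If the gate already gives that protection, halving the level buys no further control at 5% and only makes true effects harder to detect.

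The loss falls mainly on video-only versus usual care. That is one of the two comparisons in the primary objective, and the weaker one by design. At 67% power, a video that works exactly as assumed would be missed about one time in three.

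**Working it through.** **Why the gate is enough.** Write H_F for full = usual care at months 1, 3 and 6 (3 df), and H_V for video-only = usual care at the same visits (3 df). If both hold, all three arms are equal at all three visits, which is the 6-df null. The gate is therefore a 5% test of the only intersection hypothesis in the family. Closed testing rejects H_F when the gate and the F contrast are both significant at 5%, and likewise for H_V. This controls family-wise error at 5% whichever nulls are true.

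**Inputs.** Protocol 6.2: 93% and 67% at the 2.5% level, 120 per arm, mean pain 20% and 15% below usual care. Protocol 3.3: about 133 per arm. The means and covariances are in figures not shown, so noncentralities are solved from the stated powers.

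**Reproducing the plan's figures.** Power of a 3-df contrast is P(χ²₃(λ) > c), with c = 9.35 at 2.5% and 7.81 at 5%.

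- 93% at 2.5% gives λ_F = 18.09. 67% gives λ_V = 10.05.
- Ratio 10.05 / 18.09 = 0.556. The planned effects imply (15/20)² = 0.5625.
- From λ_F alone: 18.09 × 0.5625 = 10.18, giving 67.7% for video-only (stated 67%).
- From λ_V alone: 10.05 / 0.5625 = 17.87, giving 92.7% for full (stated 93%).
- With proportional effects the 6-df noncentrality is 13/12 of λ_F: 18.09 × 13/12 = 19.60, giving 93.5% (stated at least 90%).

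The protocol's powers agree with each other and with its effect ratio.

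**Power at 5%.** Before the gate at 120 per arm, video-only rises from 67% to 76.3% and full from 93% to 96.0%. Simulating the whole gated procedure, with noncentrality proportional to sample size:

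| Per arm | Gate passed | Video-only, 2.5% → 5% | Full, 2.5% → 5% |
|---|---|---|---|
| 120 | 93.4% | 66.7% → 75.4% | 91.1% → 92.5% |
| 133 | 95.8% | 72.3% → 80.3% | 94.2% → 95.2% |

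Allowing for rounding in the stated 93% and 67%, the gated 5% figures at 120 per arm are 74.9–75.9% (video-only) and 92.0–93.0% (full). Using F rather than chi-square tests moves the ungated 76.3% only to 76.4–76.5%.

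**Equivalent sample size.** Reaching 76.3% before the gate while keeping 2.5% needs about 143 per arm. Matching 75.4% through the gate needs about 141.

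**Family-wise error, simulated.**

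| Truth | As written (2.5%) | Contrasts at 5% behind the gate |
|---|---|---|
| All arms equal | 3.1% | 3.9% |
| One intervention works, the other does not | at most 2.5% | at most 5.0% |

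Contrasts at 5% *without* the gate give about 9.1% when all arms are equal, so the 5% level depends on keeping the gate.

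**The case against.** The strongest reply is that nothing here is wrong. The rule is stated consistently in the synopsis, protocol 6.1 and SAP section 9, power was computed at the same level, and a stricter valid procedure is a legitimate choice. That stands: this is a point about efficiency, and type I error is controlled as written.

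Other points have weight:

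- **Timing.** The SAP is dated July 2022, phone enrollment restarted in April 2020, the trial is open-label, and the principal investigator is unblinded. Relaxing a primary threshold this late invites challenge. The change costs no patients or data, but it does need a documented blinded decision.
- **Sample size.** The primary analysis is ITT with about 133 per arm, where the gain is about 8 points, from 72% to 80%. The 67% belongs to 120 per arm.
- **An alternative.** With Bonferroni in place, the gate is equally unnecessary. Holm on the two contrasts with no gate gives about 75.6% (video-only) and 94.1% (full) at 120 per arm, also at 5% family-wise. It is slightly better for the full arm, but it drops the overall test as the first step.
- **Carry-over.** SAP section 10 applies the same sequence to Pain Severity and to Interference, so their level would change too. The closure argument holds within each of those outcomes.
- **Outcome.** Protocol 6.2 describes power for pain severity, whereas the SAP's primary outcome is the combined severity and interference score. The absolute powers may therefore differ for the actual outcome. The error-control argument does not depend on this.

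None of these changes the conclusion that the 2.5% level is unnecessary behind the gate.

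**Conclusion.** The point holds. The plan is valid but pays for multiplicity twice. Testing each 3-df contrast at 5% behind the existing gate keeps strong 5% family-wise control. It adds about 9 points of video-only power at 120 per arm, or 8 at 133, and about 1 point for the full intervention.

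The logic of error control is exact, given valid tests at each step. The power figures assume that the stated 93% and 67% are ungated 3-df powers at 120 per arm, that effects are proportional across visits, and that large-sample tests apply.

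The closure covers the joint 3-df contrasts only. It does not license claims at single visits and does not extend to the secondary 95% intervals at each time point.

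**What to change.** In SAP section 9, replace the second-step level with: *If the 6-df test is significant at 5%, each 3-df contrast against usual care is tested at 5%; by the closed testing principle the family-wise error is 5%.* Align the protocol synopsis and section 6.1 for consistency. State in SAP section 10 whether the new level also applies to Pain Severity and Interference.

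Restate power through the gate at 120 per arm as about 92–93% (full) and 75–76% (video-only). The sponsor should recompute these from its own covariance matrix and for the combined score, and add the figures at 133 per arm.

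The SAP already provides the route. Section 4 says that key statistical decisions "will be made in a blinded review of the data", and the introduction says: "Any significant changes made to this analysis plan after study initiation will be documented herein". The documents do not show whether unblinding has occurred. If it has, the 2.5% rule should stand.

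Optionally, full versus video-only, which protocol 1.3 hypothesises but the SAP does not formally test, could be added at 5% behind the same gate with no extra alpha. Its noncentrality is only about 18.09 × (5/20)² = 1.13, so its power is about 12–13% at 120 per arm. That should be disclosed, because a non-significant result would not be evidence of equivalence.

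The cost is one rule, a recorded SAP amendment and a revised power statement, with no added patients or data.

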#### **4.3 Baseline procedures**

Baseline data collection will begin after a subject gives consent to participate in the study. The SC or RA who conducted eligibility screening and obtained verbal consent will conduct the baseline interview questionnaire during the same enrollment call. Data collection will entail questionnaires and data abstracted from the

patient's medical record. The questionnaires will be administered in an interview format. Data abstracted from the patient's EHR in Epic will occur after the enrollment phone call.

After consent is obtained and baseline data is collected by the SC or RA, the SC/RA will randomize the patient and provide a video link and instructions on how to watch the video if the patient is randomized to watch it. This is to ensure that any RA who is blind to the patient's study arm remains blinded and is able to complete follow-up interviews.

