#### *Baseline Questions and Measures*

- Access to Primary Care question
  - Question which asks whether the patient has a primary care provider
- Analgesic and Opioid use questions
  - Analgesic and opioid use questions which assess opioid use in the ED and pain medications in the past week
- Nonpharmacological pain management use questions (e.g., deep breathing)
  - Questions to assess strategies patients have used besides medication to manage pain such as mindfulness, meditation, imagery, yoga, or visiting a chiropractor

- Brief Pain Inventory-Short Form^28
  - The BPI-SF is an 11-item measure that rates pain severity and interference over the past week on a 0-10 numeric scale with higher scores reflecting more pain severity and more pain interference.
- Recovery Questions
  - Two questions to measures how well patients expect to recover from their pain and how long they estimate recovery will take.
- Prior History of Chronic Pain
  - Two questions based on the 2010 National Health Interview survey to assess if patients have a history of chronic pain.
- ENRICHD Social Support Inventory (ESSI): item 4 and 5
  - The two items on the ESSI will assess perceived social support (how much a patient feels supported) and embedded social support (whether a patient has practical help with everyday tasks)
- Single Item Literacy Screen
  - The SILS uses one question to identify limited reading ability, which is a component of health literacy. It assesses how often one needs assistance reading materials provided by a doctor or pharmacy, on a scale from “never” to “always.”
- Tobacco Screening Measure
  - This tool was developed by the University of Maryland School of Medicine and entails 2 questions to screen whether the patient has smoked cigarettes or used tobacco products ever or in the past 30 days.
- Pain Catastrophizing Scale 4-item version
  - The PCS-4 measures rumination, magnification, and helplessness related to one’s pain experience by having patients rate the degree to which thoughts and feelings are associated with their pain on a 5-point scale, ranging from “not at all” to “all the time.”
- Pain Self-efficacy Questionnaire-4 item version
  - The PSEQ 4-item questionnaire measures how confident a patient feels they can accomplish activities despite their pain on a 6-point scale where 0 is “not at all confident” and 6 is “completely confident.”

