## 5.4 Schedule of Events

Procedures	Enrollment / Baseline	Telecare (48-72 hrs after enrollment)	Week 1 Follow-up Call	1, 3, 6, and 12 Month Follow-up Call
Demographics	X			
Obtain verbal informed consent	X			
Randomization	X			
Administer educational video	i, ii			
Call with research nurse		i		
Data Collection Measures/Questions				
Assess access to primary care provider question	X			
Overview of analgesic use (opioid and non-opioid)	X		X	X
Use of other pain management strategies	X		X	X
Brief Pain Inventory-short form (pain severity only)	X			
Brief Pain Inventory-short form (pain severity and pain interference)			X	X
Pain recovery questions	X			
Prior history of chronic pain questions	X			
Pain Catastrophizing Scale-short form	X			
PROMIS Global Health-2a (prior to pain)	X			
PROMIS Physical Function (prior to pain)	X			
PROMIS Global Health-2a (including pain)	X		X	X
PROMIS Physical Function (including pain)	X		X	X
Patient Health Questionnaire (Prior to pain)	X			
Generalized Anxiety Disorder-2 (Prior to pain)	X			
Control Preference Scale	X			
Pain Self-efficacy questionnaire-4 item version	X		X	
Single Item Literacy Screen	X			
Tobacco Screening Measure	X			
Global Impressions of Change			X	X
Preparedness and Confidence questions			X	
Opioid specific questions*	X		X	X
Non-opioid analgesic questions	X		X	X
Analgesic side effects			X	X
Pittsburgh Insomnia Rating Scale			X	X
International Physical Activity Questionnaire			X	
Health Utilization questions*	X		X	X
COVID-19 activity questions				X**

i Subjects in Full intervention arm

ii Subjects in Video-only intervention arm

\*Data obtained through Electronic Health Record AND Questionnaires

\*\* month 3 only

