**Objective 2:**

[figure not shown]
[figure not shown]
[figure not shown]
To examine potential mechanisms by which the intervention influences outcomes, we will apply a structural equation model (specifically, a path analysis with manifest variables) with all variables incorporated appropriately for their scale. The model will use data from all patients and will control for demographic and clinical characteristics used for adjusting the Objective 1 model. The primary model will include direct and indirect effects of the interventions on the outcome through potential mediating variables (self-efficacy, use of specific analgesics or behaviors) to allow for assessment of whether mediation is present, and if so, if it is complete or partial. No structural relationship will be imposed relating the mediating variables to one another, beyond simple correlations. We will first test each of the path coefficients from the interventions to the mediator variables separately at the  $p=0.05$  level using chi-squared difference tests. We will then test indirect paths to assess mediation. Standard model fit indices (i.e., RMSEA, Bollen's Incremental Index, and the Tucker-Lewis index) will be reported.

As an exploratory analysis, to assess whether the use of specific medications or recovery promoting behaviors during the first week or the first month mediate pain recovery, these variables will also be examined as potential mediators following the methods described above.

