Similar longitudinal modeling approaches will be applied to evaluate treatment effects on other secondary outcome variables. Appropriate models will be applied depending on the scale of the outcome variable, but the model for fixed effects/linear component will remain consistent across outcomes. For opioid use, a binary outcome, we will apply generalized estimating equations along with a logistic link function and unstructured working covariance matrix. For analgesic-related side effect frequency and severity, physical function, overall health, sleep quality, and healthcare utilization, all quantitative measures, we will compare mean response over time by applying generalized estimating equations along with an identity link function and unstructured working covariance matrix. All comparisons will be made using appropriately specified linear contrasts, tested at the 5% significance level, and/or 95% confidence intervals.

Non-opioid analgesic use and use of other pain management strategies will be descriptively summarized by randomization group and time, without any plans to apply inferential statistical methods (hypothesis tests or confidence intervals).

Exploratory Analyses: To assess whether some groups of participants are more likely to benefit from the interventions, we will estimate and compare effects using tests of interaction for a priori identified subgroups based on gender, race, health literacy, access to a PCP, and preference for control over decision-making⁴. To assess for potentially differential intervention effects on the primary outcome across each of the subgroups, we will use ANCOVA models similar to that for the primary analysis, but with the addition of appropriate interactions between intervention groups and subgroups. Separate models will be used to assess each interaction. Interpretation of differential effects of the intervention will be limited to subgroups for which an interaction is significant at the 5% level.

⁴ After enrollment was converted to remote due to COVID, which meant that the intervention was experienced following the ED visit, the shared decision making items were dropped from the study. Thus, we will not use “preference for control over decision-making” as a variable in our models.

11. Assessing Potential Mechanisms (Objective 2)

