To address the Objective 2, we will apply structural equation models (specifically, longitudinal path analyses with manifest variables) with all variables incorporated appropriately for their scale. The structural equation models will be fit using MPlus software, version 8.3 or higher. The models will use data from all participants and will control for the same baseline variables as for the primary objective. Full maximum likelihood methods will be used, which allow for inclusion of all observed data for participants who contribute incomplete data. The primary model will include direct and indirect effects from the interventions to the longitudinal outcomes through potential mediating variables (self-efficacy and other “process-related” variables measured at the 1-week phone call) to allow for assessment of whether mediation is present, and if so, whether it is complete or partial. No structural relationships will be imposed relating the potential mediating variables to one another, beyond simple correlations. For the longitudinal outcomes, we will include Pain Severity and Interference in the model as separate variables, which we will allow to be correlated at each time point. We will first test each of the path coefficients from the interventions to the mediator variables separately at the $p=0.05$ level using chi-squared difference tests. We will then test indirect paths to assess mediation. We will compare full and reduced models (with selected paths restricted to be zero) using chi-squared difference tests. Standard model fit indices (i.e., RMSEA, Bollen’s incremental index, and the Tucker-Lewis index) will be reported.

A schematic diagram of the general model set up is shown in Figure 1 below. In this figure, straight arrows represent structural paths, curved arrows represent correlations.

12. Summary of Safety Data

Adverse events will be descriptively summarized for the ITT Population, by randomized treatment group, using frequency tables. Summaries will also be presented according to severity and perceived relatedness to the study. No inferential statistics (hypothesis tests or confidence intervals) will be presented for comparing across groups.

Figure 1. Schematic diagram of the proposed longitudinal path model.

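### The primary covariate set is carried over without own baselines: the two PROMIS outcomes lose precision (SAP 10), and baseline self-efficacy can confound the mediation path (SAP 11)

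*SAP*

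**What the plan says.** SAP 9 adjusts the primary model for nine variables: site type, baseline pain severity, age, gender, race, comorbidity score, baseline intermittent opioid use, history of chronic pain, and access to a PCP. The only patient-reported scale score among them is pain severity.

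SAP 10 extends this to the secondary outcomes, physical function and overall health among them: "the model for fixed effects/linear component will remain consistent across outcomes". SAP 11 says the Objective 2 path models "will control for the same baseline variables as for the primary objective". It names self-efficacy at the 1-week call as a mediator, alongside other process variables that it does not list.

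The Schedule of Events (Protocol 5.4) ticks the rows beginning "PROMIS Physical Function (including pain" and "PROMIS Global Health-2a (including pain" at baseline and again at follow-up. It ticks "Pain Self-efficacy questionnaire-4 item version" at baseline and week 1. Protocol 5.2 describes that scale among the baseline measures: "The PSEQ 4-item questionnaire measures how confident a patient feels they can accomplish activities despite their pain". Protocol 4.3 puts these measurements before allocation: "After consent is obtained and baseline data is collected by the SC or RA, the SC/RA will randomize the patient".

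Neither document enters any of these three baseline scores in a model.

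**The concern.** The omission has a different consequence in each section.

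- **SAP 10, precision.** Randomization protects the arm comparisons on PROMIS Physical Function and Global Health whichever covariates are used. The baseline value of the same scale is normally one of the stronger predictors of the follow-up value, so leaving it out gives up precision. The plan's own reason for its covariates is prognostic value, and its primary model already adjusts for a baseline component of its own outcome.
- **SAP 11, bias.** The arm-to-mediator path is randomized. The mediator-to-pain path is not. Someone who starts with high self-efficacy may have high self-efficacy at 1 week and less pain later, whatever the intervention does. If that holds beyond the listed covariates, the mediator-to-pain path is biased. The indirect and direct effects then move in opposite directions while the total effect stays the same. SAP 11 sets out to say whether mediation is partial or complete, and the answer could reflect a variable the trial measured before randomization.

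The first point is limited to the two PROMIS outcomes. Pain severity and opioid use already have a related baseline term. Sleep and side effects have no baseline in the Schedule of Events. The schedule lists only pain severity for the baseline BPI-SF, although Protocol 5.2 describes the 11-item form there, so interference is left aside. Healthcare utilization is ticked at baseline, but Protocol 5.1 describes only hospitalization in the preceding 30 days, so it is left aside too.

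**Working it through.** **The plan's own figures.** Protocol 6.2 gives 120 per group with up to 10% admitted: 3 × 120 / 0.9 = 400, as stated. The stated powers of 93% and 67% concern the primary outcome. They cannot be rebuilt because the means and covariances are in figures not shown, but they agree with each other. A 3-df test at 2.5% with 93% power needs a noncentrality of 18.1. Multiplying by (15/20)² = 0.5625 gives 10.2, or 67.7% power. The plan states no figure for the PROMIS outcomes or the path model, and neither point changes the primary sample size.

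**Number at 6 months.** Protocol 6.2 assumes exponential loss reaching 20% at 12 months. Retention at 6 months is 0.8^0.5 = 0.894, so 400 × 0.894 = 358, about 119 per arm.

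**PROMIS precision.** Let r be the partial correlation of baseline with follow-up score, given the nine covariates. The documents give no value; 0.2 to 0.6 is an assumed range. Own-baseline adjustment multiplies residual variance by 1 − r² and interval width by √(1 − r²). The pairwise 95% half-width under the written model is 1.96 × √(2/119) = 0.254 residual SD.

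| r | Variance factor | Width factor | Half-width (SD) |
|---|---|---|---|
| none | 1.00 | 1.000 | 0.254 |
| 0.2 | 0.96 | 0.980 | 0.249 |
| 0.3 | 0.91 | 0.954 | 0.242 |
| 0.4 | 0.84 | 0.917 | 0.233 |
| 0.5 | 0.75 | 0.866 | 0.220 |
| 0.6 | 0.64 | 0.800 | 0.203 |

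**Mediation bias.** Standardize within arm and partial out the listed covariates. Let X be arm, M0 baseline PSEQ-4, M1 the 1-week score and Y later pain:

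- M1 = a·X + g·M0 + error
- Y = b·M1 + d·M0 + error, with the true b = 0

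Omitting M0 gives an estimated b of g × d, an indirect effect of a × g × d, and a direct effect shifted by −a × g × d. The assumed inputs are g = 0.2 to 0.6, d = −0.1 to −0.3 SD per SD, and a = 0.3 SD.

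For the test of b at n = 358, with ρ = |g × d|, z = ρ√358 / √(1 − ρ²), and the rejection rate is P(Z > 1.96 − z) + P(Z < −1.96 − z).

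| g, d | Spurious path | Spurious indirect effect (SD) | z | Path test rejects | Both paths significant |
|---|---|---|---|---|---|
| 0.2, −0.1 | −0.02 | −0.006 | 0.38 | 7% | 4% |
| 0.4, −0.2 | −0.08 | −0.024 | 1.52 | 33% | 21% |
| 0.6, −0.3 | −0.18 | −0.054 | 3.46 | 93% | 59% |

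The last column comes from a simulation (4,000 runs, 119 per arm, a = 0.3). It counts trials in which the arm-to-mediator and mediator-to-pain paths are both significant. The same simulation gave 6.5%, 33% and 94% for the path test alone. With baseline PSEQ-4 in the model, the path test rejects in about 5% of runs and both paths are significant in 3% to 4%.

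A separate large-sample regression that also adjusted for baseline pain, with g from 0.3 to 0.7, gave spurious paths of −0.03 to −0.20. These returned to zero once baseline PSEQ-4 was added. The arm-to-mediator path and the total effect were unaffected.

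**The case against.** - **The PROMIS half is only a gain in precision.** A single prespecified linear component limits analyst discretion, the trial is not sized on secondary outcomes, and at r = 0.2 to 0.4 the intervals narrow by only 2% to 8%. This is fair. That half is worth doing because it is free, and it would carry little weight alone.
- **The joint result matters more than the path test.** SAP 11 tests the arm-to-mediator paths and then the indirect paths. On that reading 4% to 59% is the more relevant range. The low end shows no real inflation, and the high end needs both inputs at their most adverse. Both ranges are therefore given.
- **No correlation comes from the documents.** Baseline pain, chronic pain history and opioid use may absorb much of d. If d = 0 there is no bias, and if the arm does not move the mediator there is no spurious indirect effect.
- **Figure 1 of the SAP is not available.** A baseline mediator could be drawn there. The text of SAP 11 mentions none. Similarly, consistency across outcomes might be meant to allow each outcome its own baseline, but SAP 10 does not say so.
- **One confounder is not all of them.** Pain catastrophizing, PHQ-2 and GAD-2 are also measured at baseline and left out of the set. The return to 5% holds in a model with a single confounder. Adding PSEQ-4 closes the most direct measured route and does not make the path unconfounded.
- **The case is weaker for analgesic use and behaviors.** They come from the protocol's list, "potential mediating variables (self-efficacy, use of specific analgesics or behaviors", which the SAP supersedes, and baseline opioid use is already partly covered.

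None of this removes the omission or gives a reason for it.

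**Conclusion.** The concern holds. The written models leave out three baseline scores that are collected before randomization and that belong in them.

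- **PROMIS outcomes:** no bias; intervals 2% to 20% narrower with the fix, for r between 0.2 and 0.6.
- **Objective 2:** possible bias in the mediator-to-pain path, and so in the direct and indirect effects. With a true path of zero the spurious path is −0.02 to −0.18 SD and, with a = 0.3, the spurious indirect effect is −0.006 to −0.054 SD.

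The direction of the argument follows from the design. The size rests entirely on assumed correlations, on the listed covariates not already removing the effect, and on Figure 1 not showing a term that the text omits. Objective 2 is the stronger reason to act. The change should be made, but the primary analysis does not depend on it.

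**What to change.** Add to SAP 10: *The models for PROMIS Physical Function and PROMIS Global Health additionally adjust for the baseline score on the same scale, using the including-pain version that matches the follow-up measure.* Naming the version matters because the Schedule of Events also lists a prior-to-pain version at baseline.

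Add to SAP 11: *The path model additionally includes baseline PSEQ-4, and the baseline value of any other mediator collected at baseline (analgesic use, other pain management strategies), as predictors of the mediators and the outcomes.*

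If Figure 1 already contains these terms, or if consistency in SAP 10 was meant to allow own baselines, the same sentences make that explicit.

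The cost is one sentence in each of two sections, one degree of freedom in each PROMIS model, and one extra path per added baseline variable in each path-model equation. No new data are needed.
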